7.9.5 Vitals signs

Descriptive statistics of subject weight, BMI, vital signs (i.e. pulse rate and both systolic and diastolic blood pressure in supine and sitting positions, as well as their orthostatic change) will be tabulated by treatment group for each study visit.

Additionally, pulse rate and blood pressure will be described by medication groups of interest at baseline. See Appendix 10.3 for definitions of the medication groups.

Descriptive statistics will also be reported for the following categorised measurements:

- systolic blood pressure:
 - < 90 mmHg and a decrease of ≥ 20 mmHg
 - > 140–160 mmHg and an increase of ≥ 20 mmHg
 - > 160 mmHg and an increase of ≥ 20 mmHg
- high orthostatic change in systolic blood pressure: ≥ 20 mmHg decrease
- diastolic blood pressure:
 - < 60 mmHg and a decrease of ≥ 20 mmHg

- > 90–100 mmHg and an increase of ≥ 20 mmHg
- > 100 mmHg and an increase of ≥ 20 mmHg
- high orthostatic change in diastolic blood pressure: ≥ 10 mmHg decrease
- pulse rate:
 - < 60 bpm and a decrease of ≥ 15 bpm
 - > 100 bpm and an increase of ≥ 15 bpm
- change from baseline body weight:
 - a decrease of:
 - > 7–10%
 - > 10–20%
 - > 20%
 - an increase of:
 - > 7–10%
 - > 10–20%
 - > 20%

Drug-drug interactions will be evaluated with descriptive statistics:

- for systolic and diastolic blood pressure, with medications associated with BP changes
- for pulse rate, with medications associated with pulse rate changes

See 7.10.1 for definitions of the medication groups.

7.9.6 Physical findings and other observations

Special situations and physical examination findings will be summarised by treatment group using descriptive statistics.

7.10 Additional analyses

7.10.1 Prior and concomitant treatments

Prior and concomitant treatments will be coded using the anatomical therapeutic chemical (ATC) classification system, WhoDrug version V201909. The number and percentage of subjects using concomitant treatments at baseline will be summarised by pharmacological subgroup and chemical substance.

The following categories define groups of interest used in safety subgroup analyses:

1. Medications associated with hypotension / decrease in BP
2. Medications associated with hypertension / increase in BP
3. Medications associated with tachycardia / increased heart rate
4. Medications associated with bradycardia / decreased heart rate
5. Medications known to affect QT interval

The medication groups have been derived from validated databases: SIDER 4.1, 2015 (<http://sideeffects.embl.de/>) for medications affecting BP and HR; and CredibleMeds for medications affecting QT (<https://www.crediblemeds.org/>). Only medications with a reported frequency > 0% (in SIDER) or those in a “known risk” category (in CredibleMeds) were

included in the lists. Finally, riluzole and edaravone were not be included in any of these groups; they are covered as separate groups of their own. See Appendix 10.3 for full lists of product names used to define the categories.

7.10.2 Suicidality

Suicidality will be summarised at each visit by treatment group using descriptive statistics. Additionally, suicidality at any point over the course of the study will be described, and tested for a difference between the treatment groups with Fisher's exact test.

7.10.3 COVID-19

The number of subjects affected with any changes to study visit procedures, the number of protocol deviations, and study visits performed as a telephone contact rather than a protocol-specified on-site visit due to COVID-19 will be summarized by treatment group with descriptive statistics.

Both confirmed and suspected infections of COVID-19 will be reported as adverse events. The number of affected subjects will then be found as part of regular AE reporting (see 7.9.2).

In addition to appearing in standard reporting, protocol deviations and AEs related to COVID-19 will also be summarised in a dedicated section.

We expect precautionary measures to result in an increase of missing data for the remainder of the study. This will primarily affect Week 48 visits, and particularly measurements that cannot be performed over the phone, such as the SVC. Missing data due to COVID-19 will be treated the same as other missing data, following the procedures specified in in 6.2.5.

Efficacy measurements that were collected after the World Health Organization declared the COVID-19 outbreak a pandemic on March 11, 2020 will be flagged in the data. The potential impact of the pandemic on the treatment effect will be evaluated by including a term for whether the measurement was taken before or after the pandemic declaration in the MMRM for SVC and for ALSFRS-R. These analyses will be performed without any missing data imputation. Descriptive statistics for SVC and ALSFRS-R will be reported by visit, treatment group, and timing with respect to the pandemic declaration.

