6.2.14 Subgroups

Subgroups will be analysed for evidence of a differential treatment effect. A treatment-by-subgroup interaction term will be added to the statistical model, and the stratification factor, if present, will be removed. Subgroups defined by the following variables will be investigated:

1. Age (< 65, 65–74, ≥ 75)
2. Sex (male, female)
3. Race (white, non-white)
4. Country
5. Region (North America, rest of the world)
6. Site of onset (bulbar, spinal)
7. Edaravone use (yes, no)
8. Riluzole use (yes, no)
9. Combination of edaravone and riluzole use (4 groups)
10. Below median disease duration (time from symptom onset to randomization)
11. Above median time from symptom onset to diagnosis
12. Acetylation status (slow, fast; see 7.7)
13. Renal impairment status (see 7.9.3)
14. Hepatic impairment status (see 7.9.3)
15. Below median SVC (sitting) at screening
16. Below median SVC (supine) at baseline
17. King's clinical stage at baseline (see 7.5.2.1)
18. Below median ALSFRS-R at baseline
19. ALS progression rate at baseline (< 1 point/month, ≥ 1 point/month)
20. ALS progression rate at baseline (observed tertiles)
21. Dose change category (see section 7.4)

Subgroup analyses will be performed for the primary efficacy endpoint, the time to respiratory event endpoint, and the slope of change in the ALSFRS-R total score endpoint. Ad-hoc analyses of other endpoints may also be performed, and included in the study report.

Summary of AEs and AESIs will be presented in the subgroups of: age; sex; race; BMI; edaravone use; riluzole use; acetylation status; baseline medical history groups of interest (see 7.3); baseline renal and hepatic impairment status; and baseline King's clinical stage.

Adverse events will be summarised by patients having heart rate increase related dose changes. Drug-drug-interactions with medication groups of interest (see 7.10.1) will be evaluated for blood pressure, pulse rate, and QT interval. Dose changes will be further presented by acetylation status.

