7.5.1 Primary efficacy variable(s)

7.5.1.1 Slow Vital Capacity

The primary efficacy variable will be change from baseline SVC, measured in the supine position (SVC [supine]), through the Week 12 visit (Visit 5). SVC is defined as the maximum volume of air that the subject can exhale slowly after slow maximum inhalation. The raw SVC volume is measured in litres. The SVC variable used in the analyses is derived from the raw SVC volume, and measured as a percentage of the predicted (normal) volume for age, height and sex. Predicted values used for the calculation are derived based on the global lung function 2012 equations (Quanjer PH et al., 2012).

SVC will be assessed in both the sitting and supine position at the screening visit. Sitting SVC is used for an inclusion criterion (sitting SVC between 60–90% of the predicted value), and supine SVC is assessed to ensure that the subject is able to perform it successfully when entering

the study. At further study visits, SVC (supine) will be assessed in the morning, before administration of the study treatment. The analysis will use the best read from up to 8 attempts, as determined by the central analysts' assessment. Only the value from the best read will be included in the study's database. If even the best read is determined to be of unacceptable quality (BTRGRCD = "U"), it will be treated as missing data in the statistical analysis.

A mixed model for repeated measures (MMRM) will be used to evaluate the change from baseline SVC (supine) in the primary efficacy analysis. The model will include: fixed effects for planned treatment, randomization stratum, study visit and a visit by treatment interaction; random effects for subject and centre; and the baseline SVC (supine) value as a covariate.

Should the model estimation fail to converge, the following steps will be taken sequentially to simplify the model structure until convergence is achieved:

1. The random effect for centre will be dropped.
2. The structure of the covariance matrix for the subject effect will be changed from unstructured to: 1) Toeplitz (TOEP); 2) first-order autoregressive (AR(1)); 3) compound symmetry (CS).

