7.5.4.9 Adjust for riluzole use at baseline

Method:

- Include a term in the model for riluzole use at baseline.
- Assume no interaction effects.

Analyses that will be adjusted:

- Primary analysis SVC MMRM.
- Slope of change in the ALSFRS-R respiratory domain through 48 weeks

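### As written, the COVID-19 model in SAP 7.10.3 has no treatment-by-period term, so it cannot estimate the change in treatment effect that it is meant to evaluate

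*SAP*

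**What the plan says.** SAP 7.10.3 (COVID-19) states its aim: "The potential impact of the pandemic on the treatment effect will be evaluated". The impact is to be "evaluated by including a term for whether the measurement was taken before or after the pandemic declaration", in the repeated-measures models for SVC and ALSFRS-R. On missing data it adds: "These analyses will be performed without any missing data imputation". Alongside the model there is one descriptive commitment: "Descriptive statistics for SVC and ALSFRS-R will be reported by visit, treatment group, and timing with respect to the pandemic declaration".

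The model being extended is described in SAP 7.5.1.1. Its fixed part has "fixed effects for planned treatment, randomization stratum, study visit and a visit by treatment interaction", plus the baseline value as a covariate. The same section extends it to all visits through 48 weeks, with a treatment contrast at each visit.

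Two other places show how the SAP words such terms. For effect modification, section 6.2.14 says "A treatment-by-subgroup interaction term will be added to the statistical model"; pandemic timing is not among the 21 subgroup variables listed there. For covariate adjustment, section 7.5.4.9 adds a term for riluzole and says "Assume no interaction effects". No treatment-by-timing interaction appears anywhere in the SAP.

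**The concern.** The aim and the model do not match. Asking whether the pandemic altered the treatment effect is asking whether the treatment difference after the declaration differs from the difference before it. A before/after main effect moves both groups by the same amount and leaves the difference between them unchanged at any given visit.

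At stake is the one modelled check that the SAP offers on this question. Protocol 6.6 commits the study report to assessing how the exceptional COVID-19 measures affected the results. SAP 7.10.3 handles COVID-related missing values like any others, and the imputation model in 6.2.5 has no pandemic indicator. If the main-effect model were taken as the answer, a nearly unchanged treatment estimate could be mistaken for evidence that the effect was stable, although it would look the same either way.

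**Working it through.** The documents give no figure for this analysis, so the check is of model structure, followed by an illustration.

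**Structure.** Write the model at visit *v* for treatment *T* (0/1) and period *P* (0 before, 1 after), leaving out the other terms:
- As written: mean = a_v + b_v·T + c·P. The treatment difference is b_v when P = 0 and b_v when P = 1. Nothing in the model measures a change.
- With the interaction: mean = a_v + b_v·T + c·P + d·T·P. The difference is b_v before and b_v + d after, and *d* is the quantity asked for.

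**Borrowed inputs** (SAP 5, planned for the 12-week comparison and used here only for scale): effect 3.6 points, SD 10, 164 per group, 90% power, 450 randomised 2:1, about 20% dropout. Check: 2 × (1.960 + 1.282)² × 10² / 3.6² gives 163 per group by the normal formula, and t-test power at 164 per group is 90.2%. Dropout of 20% leaves 0.8 × 300 = 240 and 0.8 × 150 = 120, with power 89.5%. The design inputs are consistent.

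**What the main-effect model returns.** Assume one visit, 30% of records after the declaration, and an effect of 3.6 before and 0 after.
- Expected treatment estimate: 0.7 × 3.6 + 0.3 × 0 = 2.52. In 4,000 simulated trials it averaged 2.48 without the period term and 2.48 with it.
- A true constant effect of 2.52 also gave 2.48 and 2.48. The treatment estimate cannot separate the two cases.
- Expected period coefficient: (2/3) × (−3.6) = −2.4; simulated −2.41. When the effect is unchanged but both groups fall by 2.4, it was −2.39. When the effect vanishes but both groups also shift by +2.4, it was −0.02. The period coefficient does not separate the cases either.
- The interaction model gave 3.56 before and a change of −3.60, which recovers the truth.

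**Seven-visit version** (300 runs; assumed correlation 0.6, known covariance, complete data, half of Week 48 and a fifth of Week 36 records after the declaration). With the effect lost after the declaration, the Week 48 difference was 1.72 with and without the period term, and the Week 12 difference was 3.58. The fall is visible, but the model assigns it to visit. The interaction model estimated the change as −3.65 (true −3.6).

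**Precision of the interaction at a single visit.** SE = SD × √[(1/240 + 1/120) / (f(1 − f))], where *f* is the share of records after the declaration. The 95% half-width is 1.96 × SE.

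| f | SE, SD 8 | Half-width | SE, SD 10 | Half-width |
|---|---|---|---|---|
| 10% | 2.98 | 5.8 | 3.73 | 7.3 |
| 20% | 2.24 | 4.4 | 2.80 | 5.5 |
| 30% | 1.95 | 3.8 | 2.44 | 4.8 |

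Every half-width exceeds 3.6. Power to detect complete loss of a 3.6-point effect runs from about 16% (SD 10, f = 10%) to about 45% (SD 8, f = 30%; 3.6/1.95 = 1.84, and Φ(1.84 − 1.96) ≈ 0.45). The seven-visit model did better, with SE about 1.24 and power about 0.8, but only under its assumed correlation and complete data.

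**The case against.** Five points can be made for the plan.

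- **The wording is open.** The SAP does not say main effect, and unlike section 7.5.4.9 it does not rule interactions out. This has some force: the authors may say that an interaction was implied. But sections 6.2.14 and 7.5.1.1 name interactions where they are wanted, so a main effect is the plain reading, and on either reading the sentence needs correcting.
- **The model is not blind to late changes.** A reader might infer that it fits a single treatment effect for the whole study. It does not, because treatment effects are visit-specific. The SAP expects disruption mainly at Week 48, and Protocol 6.6 covers Weeks 36, 48 and end of study, so a lost effect would lower the late contrasts. What stands is narrower: the model cannot attribute that fall to the pandemic.
- **Descriptive output exists.** A reader might infer that no sign of a change could appear anywhere. The planned summaries by visit, group and timing would show the relevant cells, but without a modelled contrast or interval.
- **The main-effect model has a use.** It shows whether the treatment estimate moves after adjustment for timing. That is a legitimate question, but not the stated one.
- **The interaction will be weak.** This stands. Observed Week 48 supine SVC may well be fewer than 360: it is not measured at telephone visits (Protocol 6.6), many endpoints stop with treatment (SAP 6.2.4), and this analysis uses no imputation.

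**Conclusion.** The mismatch is real. On its plain reading, the model in SAP 7.10.3 contains no parameter for the question it is assigned, and adding the period term leaves the treatment estimate essentially where it was whether or not the effect changed. This is an unsuitable method for the stated aim, not only missing detail.

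The consequence is limited. A reader might infer that the primary result is at risk; the documents do not support that. The analysis is supportive and sits outside the testing hierarchy, and no primary or hierarchical test, significance level or sample size depends on it. Nor do the figures support expecting a decisive answer from the interaction: single-visit standard errors of about 2 to 4 points give half-widths of about 3.8 to 7.3.

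Those figures rest on assumed shares of records after the declaration, an assumed SD range of 8 to 10, and subject numbers taken from the 12-week dropout allowance. They apply to SVC only; nothing was calculated for ALSFRS-R. The SAP does not say whether the 12-week or 48-week model is meant. Enrolment dates are not given, but the visits named in Protocol 6.6 suggest that few or no Week 12 records fall after the declaration, so the interaction is likely to be informative only in the 48-week models.

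**What to change.** In SAP 7.10.3:

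1. Say that the 48-week SVC and ALSFRS-R models are meant, and add a treatment-by-period interaction to each.
2. State the assumption that the change in treatment effect is common across the affected visits, mainly Weeks 36 and 48.
3. Report the treatment difference at Week 48 before and after the declaration, and their contrast, each with a 95% confidence interval.
4. Keep the main-effect model and describe it as an adjustment for timing.
5. Label the interaction analysis exploratory, and state that a non-significant interaction is not evidence of no impact.

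The cost is one further term per model and its contrasts; the before/after flag and the models are already planned. The downside is an imprecise estimate that could itself be over-read, which item 5 addresses. Nothing else in the plan has to change.

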7.11 Changes from the clinical study protocol

Specification of the statistical model used in the primary efficacy analysis has been clarified.

All references to "treatment arm" have been changed to "treatment group" instead, to be consistent with the terminology used in the study's title.

Statistical hypotheses have been reworded to match model parameters. The core of the content remains unchanged.

Changed wording in the "data sets to be analysed" section to refer to "important protocol deviations" rather than "relevant major protocol deviations" when talking about the per-protocol

population. This change was made to be consistent with terminology across study communication. The core meaning remains unchanged.

Per-protocol analyses will be conducted in two separate PP populations, depending on the endpoint: PP up to week 12, and PP up to week 48. As key endpoints are assessed at different time points during the study, this provides better control for excluding subjects with deviations that could have affected the efficacy analyses.

Expanded interim analysis section to cover recommendation process in more detail.

Unacceptable quality SVC measurements will be excluded from the primary analysis.

Additional endpoints:

1. Time to any assistive device
2. Time to any respiratory assistive device
3. Time to continuous use of NIV during the night
4. Time to continuous use of NIV during the day and night
5. Time to tracheostomy, continuous ventilator dependence, or death

Additional analyses:

1. King's clinical stage will be estimated from the ALSFRS-R.
2. Restricted mean survival time will be described for time-to-event endpoints.
3. Dose change profiles will be described.
4. Correlations for biomarkers will be described, in a separate report.
5. Concentration-effect plots will be shown for SVC and QTc vs. OR-1896.
6. Adverse events will be reported by timing with respect to starting treatment, OR-1896 concentration at the Week 4 visit, and dose change profile.
7. Incidence rates will be reported for AEs.
8. Groups of TEAEs of special interest will be reported.
9. Confidence intervals for incidence proportions, incidence rates, risk ratios and incidence rate ratios will be reported for AESIs.
10. Narrative descriptions will be written for deaths, TESAEs and other significant TEAEs.
11. AEs will be reported in safety subgroups.
12. Many new categorical analyses for laboratory results will be included.
13. Cardiac safety will be assessed by modelling OR-1896 dose-response with $\Delta\Delta\text{QTcF}$.
14. Groups of concomitant medications of interest will be reported.
15. Medical history groups of interest will be reported.
16. Difference in suicidality between the treatment groups will be tested.
17. Effects of COVID-19 will be summarised.

ANOVAs will not be used to evaluate the effect of acetylation status on metabolites or HR.

MMRMs will not be used to examine treatment effects on vital signs or 12-lead ECG parameters or laboratory results.

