8.4.8.2 Clinical safety analysis

Vital signs (supine and orthostatic HR, systolic and diastolic BP) as well as standard 12-lead ECG variables will be tabulated by treatment. Potential treatment effects will be analysed using the MMRM. The number of subjects with QTc interval prolongation will be classified and summarised. The details of the MMRM model and categorical analyses will be defined in the SAP. Abnormal ECG findings, special situations and physical examination findings will be summarised by treatment group using descriptive statistics.

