6.2.2 Significance level and confidence intervals

Two-sided tests with a significance level of 5% will be used throughout the analyses. Corresponding 95% confidence intervals will be calculated for model-based contrasts, comparing the active treatment to placebo, using model-based standard error estimates.

The study has interim analyses that allow early stopping for futility, but not for efficacy. Therefore, we do not make adjustments to the significance levels in the final analyses.

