6.2.15 Descriptive statistics

The following statistics will be provided for continuous variables: number of observations, mean, standard deviation (SD), minimum, median and maximum. For categorical variables, frequency counts and percentages will be presented.

Mean, median and SD values will be presented to one more decimal place than the raw values. Minima and maxima will be presented as they appear. Percentages will be rounded to the nearest single decimal place, with the exception of 0 and 100, which will be presented as integers.

When descriptive statistics are reported by treatment group, data for a pooled total arm will also be reported, unless otherwise specified.

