In addition to standard AE reporting, detailed characteristics will be reported for AESIs:

1. SAE status
2. Need for concomitant medications
3. Severity
4. Changes in dosage
5. Outcome
6. Timing with respect to starting treatment

7. Duration of event
8. Safety subgroups (listed in 6.2.14)

Further, for AESIs, 95% confidence intervals (CIs) will be reported for incidence proportions and incidence rates, and risk ratios and incidence rate ratios (with 95% CIs) between the treatment groups will be estimated.

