 - Mild: 110–129 g/L
 - Moderate: 80–109 g/L
 - Severe: < 80 g/L

Haematocrit levels in blood (Cohen et al, 2017):

- Women:
 - Low: < 37%
 - High: > 47%
 - Normal: 37% to 47%
- Men:
 - Low: < 42%
 - High: > 52%
 - Normal: 42% to 52%

Erythrocytes count in blood (Dean, 2005):

- Women:
 - Low: < $3.5 \times 10^{12}/L$
 - High: > $5.5 \times 10^{12}/L$
 - Normal: $3.5\text{--}5.5 \times 10^{12}/L$
- Men:
 - Low: < $4.3 \times 10^{12}/L$
 - High: > $5.9 \times 10^{12}/L$
 - Normal: $4.3\text{--}5.9 \times 10^{12}/L$

7.9.4 12-lead ECG

Descriptive statistics of standard 12-lead ECG variables and abnormal ECG findings will be tabulated by treatment group for each study visit.

QT values will be corrected (QTc) according to Bazett's (QTcB) and Fridericia's (QTcF) formulae. Disjoint comparisons of QTc values to the following thresholds will be summarised:

1. Absolute values > 450 ms, > 480 ms, and > 500 ms.
2. Changes from baseline > 30 ms, and > 60 ms.

Cardiac safety will be assessed by modelling the dose-response of post-dose OR-1896 concentration vs. $\Delta\Delta\text{QTcF}$ at each visit with PK samples. $\Delta\Delta\text{QTcF}$ is defined as the difference between change from baseline between placebo and treatment, where the placebo effect is estimated for each visit with an ANOVA model.

Disjoint comparisons of Masterscope heart rate (EGHRMS) changes from baseline to the protocol-defined thresholds of > 20 bpm and > 30 bpm will be summarised by treatment group, visit, and dose level at the visit.

For subjects whose dose-level is increased at Week 2, changes in Masterscope heart rate between the measurements taken before dosing at the Week 2 and Week 4 visits will be described.

For subjects whose dose-level is reduced, changes in Masterscope heart rate between the last measurement on the higher dose and the following measurement on the lower dose will be described.

The correlation between OR-1896 concentration and post-dose Overread heart rate (EGHROR) will be described with semi-log scatterplots at each study visit.

Drug-drug interactions with medications known to affect QT interval (see 7.10.1) will be evaluated for QT, QTcF and QTcB with descriptive statistics.

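### The SAP drops the protocol's MMRM of vital signs and ECG without a reason, leaving no pre-specified, baseline-adjusted treatment difference in bpm or mmHg with a confidence interval

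*SAP*

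**What the plan says.** Protocol 8.4.8.2, on vital signs and standard 12-lead ECG variables, is unconditional: "Potential treatment effects will be analysed using the MMRM". It leaves the model details to the SAP. For laboratory values, Protocol 8.4.8.3 makes the same model optional.

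SAP 7.11 lists the change: "MMRMs will not be used to examine treatment effects on vital signs or 12-lead ECG parameters or laboratory results". Neither that section nor the revision history gives a reason.

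What the SAP keeps for heart rate and blood pressure:

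- **ECG (7.9.4):** "Descriptive statistics of standard 12-lead ECG variables and abnormal ECG findings will be tabulated by treatment group for each study visit". Heart-rate changes are also compared "to the protocol-defined thresholds of > 20 bpm and > 30 bpm will be summarised by treatment group, visit" and dose level. Heart-rate change around dose adjustments is described, and OR-1896 is plotted against heart rate.
- **Vital signs (7.9.5):** "Descriptive statistics of subject weight, BMI, vital signs" by group and visit, plus categorical summaries.
- **Adverse events (7.9.2):** increased heart rate, palpitations and hypotension are events of special interest, for which "risk ratios and incidence rate ratios (with 95% CIs) between the treatment groups will be estimated".
- **PK/PD:** a population model is planned and reported separately (SAP 7.6). The exploratory objective in SAP 3.2.2 includes heart rate.

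**The concern.** Protocol 1.3.2 names increased heart rate and palpitations as potential risks of oral levosimendan. Heart rate decides whether the dose goes up, comes down or is stopped (Protocol 5.3.2 and 4.5). Safety over 48 weeks is part of the secondary objective. Protocol 1.1 cites earlier rises of about 8 bpm against placebo in heart failure and 6–8 bpm in stroke/TIA patients, and blood-pressure falls of about 5–7 mmHg in the latter. The natural safety number from a 48-week randomised comparison is how many bpm, how many mmHg, and with what uncertainty. The protocol promised the model that yields it, and the SAP removes that model.

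The by-visit threshold counts have a further limit. A subject stopped by the heart-rate rule continues only for ALSFRS-R, ventilatory support and survival (Protocol 6.1.6), so later rows no longer contain that subject. A proportion ever above the threshold on treatment keeps such subjects.

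**Working it through.** **Does any remaining output give the missing number?** SAP 6.2.2 attaches intervals to models: "Corresponding 95% confidence intervals will be calculated for model-based contrasts, comparing the active treatment to placebo". No heart-rate or blood-pressure model is left in the SAP. SAP 6.2.15 defines the descriptive tables: "The following statistics will be provided for continuous variables: number of observations, mean, standard deviation (SD), minimum, median and maximum". They contain neither a between-group difference nor an interval. The remaining ECG model relates OR-1896 concentration to placebo-corrected QTcF change, in ms. The special-interest ratios have intervals but count reported events, not measured values. The separate PK/PD model describes exposure and response, not the randomised contrast. So the number is absent.

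**Size.** The plan states no figure to reproduce. The documents give no SD for heart rate or blood pressure, so every SD below is an assumption.

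Subjects observed at Week 48, from 300 and 150 randomised:
- Protocol 8.2 allows about 20% dropout: 300 × 0.8 = 240 and 150 × 0.8 = 120.
- A lighter case is 259 and 133, that is 392 of 450, or 12.9% lost (assumed).

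Let b be the between-subject SD, w the day-to-day SD, r the recording SD and e the SD of individual response on levosimendan. The ECG baseline is the mean of three recordings (SAP 6.2.7).

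- Baseline variance V0 = b² + w² + r²/3. Follow-up variance V1 = b² + w² + r². Covariance = b².
- Change-score variance C = V0 + V1 − 2b².
- Baseline-adjusted variance A = V1 − b⁴/V0.
- 95% half-width = 1.96 × √[(X + e²)/n1 + X/n2], with X = A (adjusted) or X = C (by hand from change tables).

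Heart rate: b 6–12, w 4–8, r = 3, e = 6 bpm. Systolic pressure: b 10–15, w 8–12 mmHg, r = e = 0. Smallest and largest cases:

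| Case | A | C | n | Adjusted | By hand |
|---|---|---|---|---|---|
| Heart rate, b 6, w 4 | 37.4 | 44 | 259/133 | 1.47 | 1.57 |
| Heart rate, b 12, w 8 | 118.7 | 140 | 240/120 | 2.51 | 2.70 |
| Systolic, b 10, w 8 | 103.0 | 128 | 259/133 | 2.12 | 2.37 |
| Systolic, b 15, w 12 | 231.8 | 288 | 240/120 | 3.34 | 3.72 |

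If a further 20% of Week 48 heart-rate readings were remote and set aside (assumed share), 2.51 becomes 2.51 × √(1/0.8) = 2.80 bpm. Heart rate therefore runs from about 1.5 to 2.8 bpm. Systolic pressure runs from 2.1 to 3.3 mmHg before any such exclusion; the same 20% would lift its upper end to 3.34 × 1.118 = 3.7.

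Gain from adjustment, 1 − adjusted/by hand, over the whole grid:
- Heart rate: 2.0% (b 12, w 4) to 15.5% (b 6, w 8).
- Systolic pressure: 5.7% (b 15, w 8) to 16.0% (b 10, w 12).

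The formula uses baseline and Week 48 only. An MMRM also draws on the intermediate visits, so it could do slightly better when Week 48 is missing.

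**The case against.** The strongest reply is that this is a disclosed choice with little numerical consequence. Much of it stands. SAP 7.11 lists the change openly, and other entries there also lack a reason, such as the dropped acetylation ANOVAs and the exclusion of unacceptable-quality SVC. The named cardiovascular risks do get randomised comparisons with intervals, as events. A reader can form a crude difference from the reported n, mean and SD, and adjustment narrows its interval by only a few to 16 percent. That hand calculation does need change-from-baseline tables, and SAP 7.9.4–7.9.5 do not say whether the mean tables show change or raw values.

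Some stronger readings are tempting but unsupported:

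- **That the trial has no controlled heart-rate comparison with an interval.** The special-interest ratios in SAP 7.9.2 are exactly that, for reported events. Only the measured scale is missing.
- **That heart-rate-guided stopping makes the remaining tables seriously misleading.** The documents give no SDs and define no safety estimand, so the size of any bias cannot be established from them. Nor can one show that a model assuming missing at random would recover the on-treatment effect here.
- **That all the dropped models breach the protocol.** The laboratory MMRM was optional, and QTcF keeps a concentration-response model.

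A general describe-only safety policy does not explain the omission, however. The same SAP adds a Fisher's exact test for suicidality and interval estimates for special-interest events.

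**Conclusion.** The point holds as a cheap improvement, not as an error that changes a result. An unconditional protocol commitment was withdrawn without explanation, and nothing left in the SAP supplies a baseline-adjusted difference in bpm or mmHg with a confidence interval. The loss is mainly a pre-specified estimate, with its uncertainty, for the main known risk. The loss of precision is modest: half-widths of about 1.5–2.8 bpm and 2.1–3.3 mmHg, against 2–16% more when worked out by hand from change tables. These figures rest on assumed SDs, 13–20% attrition and, for the upper heart-rate figure, an assumed 20% of readings set aside as remote. The textual finding needs none of these assumptions. The efficacy analyses and their type I error are untouched.

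**What to change.** In SAP 7.9.4–7.9.5, before the treatment code is opened:

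1. Restore an estimation-only MMRM of change from baseline in pre-dose ECG heart rate (Masterscope, the source already used for the thresholds) and in supine systolic and diastolic pressure. Include baseline, stratum, visit, treatment and treatment-by-visit. Report the difference with its 95% CI at each visit, and state that it targets the on-treatment effect under missing at random.
2. Add the between-group difference, with 95% CI, in the proportion of subjects ever above 20 and ever above 30 bpm on treatment.
3. Leave COVID-19 remote readings out of the main model and include them in a sensitivity run. Under Protocol 6.6 a remote ECG uses a local device and is pre-dose only by preference, and home blood-pressure devices are possible with sponsor approval.
4. Amend SAP 7.11 to match, with a reason for the parts of the protocol analysis that stay out: orthostatic values, post-dose readings, PR and QRS. The QTcF and laboratory models can remain out.

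The cost is one edited sentence, a short paragraph, three models, one sensitivity run and two proportion comparisons on data already collected. The downside is a little more analysis work and fewer Week 36 and Week 48 readings in the main model.
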